The Effects of Additional Gluteal Control Training in Chronic Low Back Pain Patients with Functional Leg Length Inequality

Author: [name]

Adviser: [name], Ph.D.

Study Protocol

- Objectives: To investigate the effect of additional gluteal control training on improving FLLI, the symmetry of pelvic alignment, hip control ability, pain, and disability in the LBP patients with FLLI.
- Design: Double-blind randomized- control trial study design
- Methods: 48 LBP patients with FLLI were recruited randomized to the additional gluteal control training group (GT) (experimental group, 10 males and 14 females, 47.58 ± 9.42 years, n=24) or the regular training group (RT) (control group, 11 males and 13 females, 47.38 ± 11.31 years, n=24). Both groups received general physical therapy (including thermal therapy, electro-therapy, and lumbar traction) for 6 weeks, and GT group received additional gluteal control training. The primary outcomes were pelvic inclination (PI) (degree), ilium anterior tilt difference (IATD) (degree), and functional leg length inequality (FLLI) (centimeter). And the secondary outcome measures were visual analogue scale (VAS), patient specific-functional scale (PSFS), Oswestry disability index (ODI), hip control ability, global rating of change scale (GRoC), lower extremity strength (kilogram) and lower extremity flexibility (degree). Statistical analysis was performed on an intention to treat basis using two-way repeated measures analysis of variances (ANOVAs) to examine if the experimental group showed more improvement than the control group. The significance level was set at $p<0.05$.

Statistical Analysis Plan

- Two-way repeated measures analysis of variance (ANOVA) for pelvic inclination, ilium anterior tilt difference, functional leg length inequality, VAS, ODI, PSFS, muscle strength and muscle flexibility
- Statistical significance for all comparison at $P < .05$

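### Does an undefined double-blind label call for a blinding safeguard in the analysis plan?

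*Combined protocol and SAP*

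**What the plan says.** The Design bullet of the Study Protocol contains the only statement on blinding: "Double-blind randomized- control trial study design". It names no blinded role and no method.

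The Methods bullet describes the treatment contrast. On the shared care: "Both groups received general physical therapy (including thermal therapy, electro-therapy, and lumbar traction) for 6 weeks". On the difference between the arms: "GT group received additional gluteal control training". No sham or matched exercise is described for the control arm. There are 24 patients per arm.

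The three primary outcomes (PI, IATD and FLLI) are physical measurements, with no rater or instrument stated. The seven secondary outcomes are VAS, PSFS, ODI, GRoC, hip control ability, strength and flexibility.

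The analysis is by intention to treat, "using two-way repeated measures analysis of variances (ANOVAs) to examine if the experimental group showed more improvement than the control group". The Statistical Analysis Plan lists eight outcomes for that ANOVA (all but hip control and GRoC) and sets one threshold: "Statistical significance for all comparison at" P < .05. It has no blinding check and no sensitivity analysis.

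**The concern.** In an exercise trial, a double-blind label invites the question of who was blind. The therapist giving the gluteal training cannot have been. Patients in that arm knew they were exercising, although they may not have known the hypothesis or what the other arm received. Assessors and the analyst could have been blinded, but the text does not say so.

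The possible readings protect different outcomes. Blinded assessors protect PI, IATD, FLLI, strength, flexibility and probably hip control. Blinded participants protect VAS, PSFS, ODI and GRoC. A blinded analyst protects neither set at the point of measurement. If the assessors were not blind, all three primary outcomes carry a risk that the label hides. The plan reads every comparison at the same threshold, so a small difference in rating between the arms could turn a null result into a significant one with nothing in the analysis to flag it.

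**Working it through.** **Inputs.** From the documents: 24 per arm and alpha 0.05. Assumed, because the documents do not say: a two-sided test, two measurement times, complete data, and the size of any rating shift. The documents give no power, effect size or outcome SD, so there is no stated figure to reproduce.

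**Step 1: which outcomes depend on whom.** Assessor-dependent: PI, IATD, FLLI, strength, flexibility and probably hip control (6). Patient-reported: VAS, PSFS, ODI, GRoC (4). The total is 6 + 4 = 10, which matches 3 primary plus 7 secondary. In the SAP's list of 8, the split is 5 and 3.

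**Step 2: can the label be narrowed by counting readings?**
- Take four roles: participants, treating staff, assessors, analyst. There are C(4,2) = 6 pairs. Three include the treating staff, which leaves three: participants with assessors (both sets of outcomes protected), participants with analyst (assessor-dependent set exposed), and assessors with analyst (patient-reported set exposed).
- Now split off staff who give only the shared therapy. There are C(5,2) = 10 pairs, and six stay open. One of these, shared-therapy staff with analyst, leaves both sets exposed.

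The documents describe no such separate staff, so the count depends on the role list chosen. All it establishes is that the readings differ.

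**Step 3: size of the stake.** With two times, the group-by-time F is the square of a two-sample t on change scores.
- df = 24 + 24 − 2 = 46; critical t = 2.013; critical F = 2.013² = 4.05.
- SE = √(2/24) = 0.289 SD of the change score.
- Smallest significant difference = 2.013 × 0.2887 = 0.58 SD.

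With no true effect and a rating shift of b SD, the rejection rate from a noncentral t with noncentrality b/0.2887 is:

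| b (SD of change) | Rejection rate |
|---|---|
| 0 | 5.0% |
| 0.1 | 6.3% |
| 0.1923 | 10.0% |
| 0.3 | 17.4% |
| 0.5 | 39.6% |

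**Step 4: what an analytic safeguard would add.** The natural candidate is the rating shift that would just remove significance, |d| × (1 − √(4.05/F)), where d is the difference in change. Since √F = |d|/SE and √4.05 = 2.013, this equals |d| − 2.013 × SE, which is the 95% confidence limit nearest zero.

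Check at p = .01: t = 2.687 and F = 7.22, so |d| = 2.687 × 0.2887 = 0.776 SD. The formula gives 0.776 × (1 − √(4.05/7.22)) = 0.195 SD. The confidence limit is 0.776 − 0.581 = 0.195 SD. They are the same number.

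**Step 5: is the fragility special to this trial?** As a share of the observed difference, the tipping shift is 1 − (critical t)/t.

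| p | Share, 24 per arm | Share, 240 per arm |
|---|---|---|
| .04 | 4.8% | 4.6% |
| .01 | 25.1% | 24.0% |
| .001 | 42.7% | 40.7% |

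Ten times the sample leaves the shares almost unchanged. They restate the p-value.

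**Step 6: more than two times.** With three times, group-by-time is an omnibus F on 2 and 92 df (critical value 3.10). There is then no single difference in change to enter in the formula, and substituting another critical value does not repair it. The documents do not give the number of times, so such a rule might not be usable here.

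**The case for a change.** The best case for acting is that blinding is a basic design feature, that it bears on all three primary outcomes, and that defining it costs a records check and a paragraph. The Design and Methods text does not look redacted at this point, so the silence is probably real, although consent pages were removed and could say what participants were told. The arithmetic is also correct: an unblinded rater who shifts scores by about 0.2 SD would double the error rate.

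Much of this stands. The label is uninformative as written, and a reader of the results will want to know who was blind. If the records show that participants were not, VAS, PSFS, ODI and GRoC need a stated limitation. If assessors were not, PI, IATD, FLLI, strength, flexibility and hip control need one.

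What does not stand is the step from there to the analysis. Naming the blinded roles describes what was done and alters no estimate, test or decision rule. Rating bias cannot be estimated from the outcome data alone. A stricter threshold would not remove it, and the tipping shift is an ordinary confidence limit under another name. The uniform P < .05 does not cause the problem either.

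**Conclusion.** No change to the plan follows. The double-blind label is undefined, but the documents do not show it to be false. A blinded assessor together with participants unaware of the hypothesis fits everything in the text. The doubling from 5% to 10% at a shift of 0.19 SD is conditional arithmetic: it rests on two measurement times, complete data, a two-sided test and a shift for which the documents offer no evidence. The exposure of the primary outcomes cannot be sized at all, because the text does not say how or by whom they were measured.

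The gap is one that authors fill when they report the trial. They state from the records who was blinded, to what and how, write that a role is not documented where the records are silent, and attach limitations to the outcomes affected. A confidence interval for the between-group difference in change, which the same data provide in the two-time case, already tells the reader how much shift a significant result would survive. A special blinding analysis in the SAP would add no information beyond that.

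### Three primary outcomes are each tested at an unadjusted 5% level with no rule for combining them, so the trial-level error of the primary claim is uncontrolled

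*Combined protocol and SAP*

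**What the plan says.** The Study Protocol (Methods) designates three primary outcomes of equal standing: "The primary outcomes were pelvic inclination (PI) (degree), ilium anterior tilt difference (IATD) (degree), and functional leg length inequality (FLLI) (centimeter"). The purpose of the analysis is "to examine if the experimental group showed more improvement than the control group", and the level is given once: "The significance level was set at $p<0.05".

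The Statistical Analysis Plan has two bullets. The first assigns the same model to each outcome: "Two-way repeated measures analysis of variance (ANOVA) for pelvic inclination, ilium anterior tilt difference, functional leg length inequality", followed by several secondary measures. The second sets the criterion: "Statistical significance for all comparison at $P < .05".

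Neither section ranks the three primary outcomes, says whether one, a particular one or all of them must reach significance, splits the alpha, forms a composite or adjusts for multiplicity. The documents also give no correlation between the outcomes, no sidedness, no measurement times and no power target.

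**The concern.** With three primary outcomes there are three chances to meet the plan's only criterion. If a report treats one significant result as showing that the added training works, the probability of such a claim when the training has no effect exceeds the 5% attached to each test. If all three had to be significant, it would not. The two rules carry different error rates, and the plan chooses neither. A reader of a result such as one significant outcome out of three would know the error rate of that single test, but not that of the overall conclusion drawn from it.

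**Working it through.** The plan states no family-wise error and no power calculation, so there is no figure of its own to reproduce.

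**Inputs from the documents**
- Primary outcomes: 3 (Methods).
- Level per comparison: 0.05 (Methods and SAP).
- Patients: 24 per group (Methods).

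**Assumptions**
- One deciding test per outcome, the group-by-time test. A two-way repeated measures ANOVA yields group, time and interaction tests, and the plan does not say which decides. The stated question about greater improvement points to the interaction.
- Two-sided tests, since an F test does not distinguish direction.
- Equal pairwise correlation r between the three test statistics, with r = 0, 0.5 and 0.9 as illustrations.

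**1. Any one suffices, no true effect on any outcome**
- Independent: 1 − 0.95³ = 1 − 0.8574 = 0.1426, or 14.3%.
- Correlated: 1 − P(|Z₁|, |Z₂|, |Z₃| all below 1.96) for equicorrelated normals, by numerical integration: 0.1254 at r = 0.5 and 0.0836 at r = 0.9.
- Simulated t tests with 24 per group (46 df, 200,000 trials) agree: 14.1%, 12.6% and 8.4%.
- With no restriction on dependence, and still one test per outcome, the limits are 5% (complete dependence) and 3 × 0.05 = 15%.

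**2. Counting only false claims that favour the added training**
- Independent: 1 − 0.975³ = 0.0731. At r = 0.5 and 0.9: 0.0627 and 0.0418. The comparator for a single two-sided test is 0.025.

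**3. All three required**
- A false claim needs at least one outcome with no true effect to reject at 0.05, so the error is at most 5%.
- The limit is approached when one outcome is null and the other two have large effects. With those two at 1.5 SD, simulation gives 4.8% to 5.0%.

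**4. Holm procedure, no true effect on any outcome**
- A false claim requires the smallest p-value to be at or below 0.05/3 = 0.0167.
- Independent: 1 − (1 − 0.0167)³ = 0.0492. At r = 0.5 and 0.9: 0.0445 and 0.0298.

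**5. Power cost of Holm** (noncentral t, 46 df, noncentrality d × √(24/2), where d is in SDs of the change score; 80% power assumed)
- Detectable d: 0.826 at level 0.05 and 0.964 at level 0.0167.
- Power at d = 0.826: 0.800 at level 0.05 and 0.647 at level 0.0167.
- Per-outcome power under Holm at d = 0.826, by simulation: about 0.65 if only one outcome has an effect; about 0.75, 0.73 and 0.71 at r = 0, 0.5 and 0.9 if all three do.

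**The case against.** The strongest reply is that the plan never says one significant outcome makes the trial positive. It can be read as three separate questions, each with its own 5% test, and whether separate questions need family-wise control is debated. This stands in part. A report that gives all three p-values and draws three separate conclusions has a known 5% error for each. A reader might infer from the single criterion that the plan adopts an any-one rule and so runs a 14.3% error. The documents do not support that: 14.3% needs the any-one reading, independence, no effect on any outcome and one test per outcome. What remains is that all three outcomes are called primary for one comparison of improvement between groups, and nothing says how they yield a conclusion.

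A second reply is that the outcomes overlap anatomically, so the inflation must be small. No correlation is given. Nor can one be inferred from the objective, which lists "improving FLLI, the symmetry of pelvic alignment, hip control ability, pain, and disability": leg length inequality stands apart from pelvic alignment there. Even at an assumed 0.9 the any-one error is 8.4%.

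A third reply is that an all-three rule may have been intended. That would remove the inflation, but it is not written down.

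Finally, the text is in the past tense and reports the enrolled groups, so a new rule may come too late to count as prespecified. That is fair, and it affects which form of the remedy applies.

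**Conclusion.** The concern holds as a missing decision rule. Error is 5% per outcome, while error for the overall primary claim is uncontrolled. If any one result is taken as sufficient and none of the three outcomes has a true effect, that error is 14.3%, 12.5% or 8.4% at correlations of 0 and an assumed 0.5 or 0.9. These figures rest on one two-sided group-by-time test per outcome. Under an all-three rule there would be no inflation. The point should be fixed: it bears on the primary conclusion, and the repair lies in the analysis and reporting alone.

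**What to change.** Add to the SAP: *For each of PI, IATD and FLLI the primary test is the between-group difference in change from baseline to the end of the 6-week treatment; with two measurement times this is the group-by-time interaction. The three two-sided p-values are assessed by the Holm procedure at family-wise 0.05: the smallest against 0.0167, the next against 0.025, the largest against 0.05, stopping at the first that fails.* Naming one test is needed because Holm must be applied to a defined set of three p-values.

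If results are already known, which the past-tense text makes likely, report Holm-adjusted p-values beside the unadjusted ones and disclose that the adjustment was added afterwards. An all-three rule or a fixed order would also control the error, provided it was set before results were seen. Holm is suggested because it needs no ranking of the outcomes.

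The cost is power, with no added patients. At 24 per group the difference detectable with an assumed 80% power rises from 0.83 to at most 0.96 SD of change. Per-outcome power at 0.83 SD falls from 80% to about 65% if only one outcome has an effect, or to about 71% to 75% if all three do.

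### The planned repeated measures ANOVA is valid but uses no baseline covariate; a baseline-adjusted comparison would usually be more precise at almost no cost

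*Combined protocol and SAP*

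**What the plan says.** The Statistical Analysis Plan has two bullets. The first names the method and the outcomes: "Two-way repeated measures analysis of variance (ANOVA) for pelvic inclination, ilium anterior tilt difference, functional leg length inequality, VAS, ODI, PSFS, muscle strength", with muscle flexibility completing the list. The second sets the significance level at 0.05.

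The Methods bullet of the Study Protocol names the same analysis, by intention to treat, and gives its purpose: "to examine if the experimental group showed more improvement than the control group".

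Neither part mentions a baseline covariate, ANCOVA or an adjusted estimate. Neither says which ANOVA term (group, time or their interaction) decides. Assessment times are not listed, and the only time given is the length of therapy: "Both groups received general physical therapy (including thermal therapy, electro-therapy, and lumbar traction) for 6 weeks". The trial has 48 patients, 24 per arm.

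**The concern.** The question is whether one arm improves more than the other. In a group-by-time repeated measures ANOVA the interaction answers it. With one value before and one after treatment, the interaction compares mean change scores between the arms.

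A change score subtracts the whole baseline value, which amounts to fixing the slope of follow-up on baseline at 1. ANCOVA estimates that slope from the data. Unless the true slope is close to 1, the change score carries extra noise and the confidence interval is wider than it needs to be.

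In a trial of 48 patients with no stated power calculation, that precision is worth having. The baseline values are already needed for the planned ANOVA, so the gain requires no new data.

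**Working it through.** **Inputs from the documents.** 24 patients per arm; significance level 0.05, taken as two-sided because the interaction F test has no direction.

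**Assumptions, none given in the documents.** One pre and one post value; baseline SD = 1; post SD = *k*; pre-post correlation *r*; a true effect of 0.5 or 0.8 baseline SD. The plan has no figure of its own to reproduce.

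**Step 1: what the planned test is.** With two groups and two times, the interaction F equals the square of the two-sample t on change scores. In a generated data set with 24 per arm, both came to 7.877.

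**Step 2: is it valid?** In 40,000 simulated trials per setting, with *r* from 0.3 to 0.9, the change-score test rejected a true null in 4.9% to 5.0% of trials. For a true effect of 0.5 its mean estimate was 0.498 to 0.500. It is valid and unbiased.

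**Step 3: variance per patient.**
- Change score: 1 + k² − 2rk, which is 2(1 − r) when k = 1.
- ANCOVA: k²(1 − r²), multiplied by 1 + 1/44 = 45/44 for estimating the slope with 48 patients.
- Before the slope factor, the change-score variance minus the ANCOVA variance is (1 − rk)², which is never negative. For k = 1 the gross saving is (1 − r)/2.

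Example at r = 0.5, k = 1: the change score gives 2 × 0.5 = 1.00, and ANCOVA gives 0.75 × 45/44 = 0.767. The net saving is 1 − 0.767 = 23%. To match ANCOVA with 24 per arm, a change-score analysis would need 24/0.767 = 31.3 per arm.

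**Step 4: results for equal SDs (k = 1).** Power is from the noncentral t, with 46 df for the change score and 45 for ANCOVA. Each pair is change score / ANCOVA.

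| r | Gross saving | Net saving | Per arm needed by change score | Power, 0.5 SD | Power, 0.8 SD |
|---|---|---|---|---|---|
| 0.3 | 35% | 34% | 36.1 | 0.30 / 0.42 | 0.63 / 0.80 |
| 0.5 | 25% | 23% | 31.3 | 0.40 / 0.49 | 0.77 / 0.87 |
| 0.7 | 15% | 13% | 27.6 | 0.59 / 0.65 | 0.94 / 0.96 |
| 0.8 | 10% | 8% | 26.1 | 0.77 / 0.80 | 0.990 / 0.994 |
| 0.9 | 5% | 3% | 24.7 | 0.966 / 0.970 | near 1 for both |

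For equal SDs the net gain disappears above r = 2 × 44/45 − 1 = 0.956.

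The simulation agrees. The ratio of ANCOVA to change-score variance was 0.675, 0.763, 0.867 and 0.968 at r = 0.3, 0.5, 0.7 and 0.9. Simulated power for 0.5 SD at r = 0.5 was 39.3% against 49.0%.

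**Step 5: net saving when the SDs differ.**

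| r | k = 0.8 | k = 1.2 |
|---|---|---|
| 0.3 | 49% | 22% |
| 0.5 | 42% | 11% |
| 0.7 | 36% | 1.2% |
| 0.8 | 35% | −2.0% |
| 0.9 | 38% | 0.1% |

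With k = 1.2, ANCOVA is slightly less precise between about r = 0.73 and r = 0.90. The loss cannot exceed 1/44 = 2.3%, and it comes close to that only when rk is near 1.

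**Step 6: the deciding term.** The group main effect averages the pre and post values, so half of it comes from a time when no effect can exist. For the same 0.5 SD effect its simulated power was 14% to 19%. Reading that term as the result would cost far more than omitting the covariate.

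**The case against.** The strongest reply is that nothing is wrong with the planned test: the choice is between two valid estimators, and the interaction does answer the stated question. That is correct, and it is why this is an improvement and not the repair of a fault.

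The size of the gain is also unknown for this trial. The documents give no correlation, SD, effect size or number of assessments. Under equal SDs the saving runs from 34% down to 3%, and if the post-treatment SD is larger than the baseline SD it can vanish at correlations well below 0.956. This stands as a limit on the figures. It does not reverse the advice, because the possible loss is bounded at about 2% while the possible gain is much larger.

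The advice may also come too late. The Methods bullet is in the past tense and reports the realised make-up of each arm, for example "experimental group, 10 males and 14 females, 47.58 ± 9.42 years, n=24". If the analysis is finished, ANCOVA should not replace the planned test, and only a disclosed additional analysis remains.

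Finally, the unlisted assessment times and the unnamed deciding term are separate gaps in specification. They are, and the case for the covariate does not depend on them.

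**Conclusion.** The concern holds. Neither the protocol nor the SAP adjusts for baseline. With one pre and one post value, the planned interaction test is a valid, unbiased comparison of change scores that is generally less precise than ANCOVA. For 24 per arm and equal SDs, the net saving in variance is 13% to 34% at correlations from 0.7 down to 0.3, and 8% or less from 0.8 upward. All of these sizes rest on assumed correlations, SDs and effects. With three or more assessment times the interaction becomes a test with several degrees of freedom, and the figures do not apply as they stand. The change is worth making because it is cheap and its downside is small; the planned analysis is not invalid without it.

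**What to change.** - List the assessment times.
- For each outcome measured at baseline, make the efficacy test an ANCOVA of the post-treatment value on group, with that outcome's own baseline value as covariate.
- If there are several follow-ups, use a baseline-adjusted linear mixed model with one named contrast at one named time.
- Report the adjusted GT-minus-RT difference with its 95% confidence interval. State that this contrast decides, and that the ANOVA group main effect does not.
- If the data have already been analysed, keep the ANOVA group-by-time interaction as the prespecified result and report ANCOVA as a disclosed post hoc or sensitivity analysis.

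**Cost.** Before analysis: one degree of freedom per outcome and a few lines of SAP text. After analysis: one added, disclosed sensitivity analysis per outcome. No new data are needed in either case.

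### Does leaving hip control ability and GRoC out of the SAP's ANOVA list call for a change to the plan?

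*Combined protocol and SAP*

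**What the plan says.** Methods in the Study Protocol names three primary outcomes: "The primary outcomes were pelvic inclination (PI) (degree), ilium anterior tilt difference (IATD) (degree), and functional leg length inequality (FLLI) (centimeter". It then names seven secondary outcomes. Three come first: "the secondary outcome measures were visual analogue scale (VAS), patient specific-functional scale (PSFS), Oswestry disability index (ODI". The other four follow: "hip control ability, global rating of change scale (GRoC), lower extremity strength (kilogram) and lower extremity flexibility (degree".

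Hip control ability also appears in the Objectives, which concern "improving FLLI, the symmetry of pelvic alignment, hip control ability, pain, and disability in the LBP patients with FLLI".

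Two places describe the analysis.

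- **Methods** describes an intention-to-treat analysis "using two-way repeated measures analysis of variances (ANOVAs) to examine if the experimental group showed more improvement than the control group". It does not say that this applies to some outcomes and not others.
- **The Statistical Analysis Plan** has two bullets. The first assigns two-way repeated measures ANOVA to "pelvic inclination, ilium anterior tilt difference, functional leg length inequality, VAS, ODI, PSFS, muscle strength and muscle flexibility". The second reads "Statistical significance for all comparison at" P < .05.

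The documents do not give the scale or the assessment times of hip control ability or of GRoC.

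**The concern.** A reader who checks the outcome list against the SAP finds two outcomes with no line. One of them, hip control ability, is close to what the added gluteal training is meant to change, so its result will attract attention.

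GRoC looks worse. Even if the Methods sentence is read as covering every outcome, a group-by-time ANOVA does not suit a rating that patients can give only after treatment has begun. Meanwhile the second SAP bullet sets one significance level for every comparison, including any that nobody has named.

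What would be at stake is selective choice. If the GRoC test were picked after the data were seen, from candidates that often disagree, the 5% level would not hold for that outcome. For hip control ability, a reader might doubt whether a result on a stated objective had been planned.

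**Working it through.** **1. Outcome count.** The inputs are the lists in Methods and in the first SAP bullet. Muscle strength and flexibility in the SAP are matched to lower extremity strength and flexibility in Methods.

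| Outcome | Role in Methods | In the SAP list |
|---|---|---|
| Pelvic inclination | primary | yes |
| Ilium anterior tilt difference | primary | yes |
| FLLI | primary | yes |
| VAS, PSFS, ODI | secondary (3) | yes |
| Strength, flexibility | secondary (2) | yes |
| Hip control ability | secondary, and an objective | no |
| GRoC | secondary | no |

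The protocol has 3 + 7 = 10 outcomes and the SAP lists 3 + 3 + 2 = 8. The two missing outcomes are 2 of 7 secondary and 0 of 3 primary. The SAP adds no outcome that the protocol lacks. The documents give no power or sample-size figure to reproduce.

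**2. Hip control ability.** Methods lists all ten outcomes and then gives one unrestricted analysis sentence. On a plain reading, hip control ability is analysed by two-way repeated measures ANOVA. That is also what anyone completing the SAP list would write for a continuous score. The documents do not confirm that the score is continuous, but nothing in them suggests otherwise.

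**3. GRoC under the general sentence.** There are 48 patients, and the model has patient, time and group-by-time terms.

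- One rating each: 48 observations and 48 patient parameters leave 48 − 48 = 0 residual df. There is no time factor and so no interaction.
- Two post-treatment ratings each: 96 observations and 48 + 1 + 1 = 50 parameters leave 96 − 50 = 46 residual df, with 1 df for the interaction. The model fits, but the interaction tests a shift between two later ratings, not greater improvement than control.

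So the ANOVA does not serve GRoC, and an analyst must choose a between-group comparison.

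**4. How much that choice matters.** This was simulated with 24 per group, two-sided 5% tests and rounded, clipped normal ratings. All of the following are assumptions, because the documents give none of them:

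- scale −7 to +7, control mean 3, SD 2.5, cut-offs 2 to 5;
- scale −5 to +5, control mean 2, SD 2, cut-offs 1 to 4;
- scale −3 to +3, control mean 1, SD 1.3, cut-offs 1 and 2.

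Ranges over the three scales and repeated runs:

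| Quantity | Result |
|---|---|
| Mean and rank tests disagree, no effect | about 1.4% to 1.6% |
| Mean and rank tests disagree, true difference 0.8 SD | about 4% to 5% |
| Power at 0.8 SD, mean or rank test | about 72% to 75% |
| False positives, better of mean and rank test | about 5.3% to 6.2% |
| False positives, those two plus one cut-off | about 8% to 9% |
| False positives, those two plus every assumed cut-off, uncorrected chi-square | about 11% to 17% |
| The same full search with continuity correction | about 7% to 9% |

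The two ordinary choices nearly always agree, and even picking the better one barely moves the error rate. The larger figures come from a search over dichotomies.

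**The case for a change.** The strongest case for a change is that the gap is plain on the page and cheap to close. Two or three lines would settle it, one of the two outcomes is a stated objective, and GRoC has no workable method on either reading of the documents. If improved were defined at a cut-off chosen afterwards, the cost would be visible. At a true difference of 0.8 SD a cut-off analysis has about 40% to 62% power, against 72% to 75% for the mean or rank test. The full set of candidate tests, with every cut-off included, fails to agree in about 40% to 63% of trials.

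Part of this stands. The count is right, and GRoC does need a method that the plan does not state. The rest does not carry. The disagreement and the inflated error rate require a search over two to four cut-offs, and nothing in the documents points to a responder analysis of GRoC. For hip control ability, the proposed line would repeat the method that Methods already gives. The shared significance level in the second SAP bullet has no separate consequence here.

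The benefit would also be limited. Methods is written in the past tense and reports the age and sex of both groups, so a line added now might only earn the analyses a post hoc label.

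**Conclusion.** No change to the plan follows. The SAP line omits two of ten outcomes, both secondary. One is reasonably covered by the unrestricted sentence in Methods. The other, GRoC, would be filled by a standard comparison of two groups of 24, where the usual candidates differ in about 1% to 5% of trials and choosing between them gives about 5.3% to 6.2% false positives. The methods for all three primary outcomes are stated and unaffected, and nothing here makes the analysis of the eight listed outcomes wrong.

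This rests on three assumptions: that hip control ability is a score suited to ANOVA, that GRoC behaves roughly like the assumed scales, and that it is compared as a rating rather than split at a cut-off chosen after the data were seen. A published GRoC result based on an unexplained cut-off should be read with caution, but that would be a question about the report, not a fault in this plan.
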